6. WITHDRAWAL OF PARTICIPANTS

6.1 Withdrawal criteria

A participant may be withdrawn from the study if they meet the following criteria:

- It is deemed in the participant's best interest based on the Investigator's clinical judgment.
- The sponsor decides to terminate the study.
- A new health condition arises that necessitates withdrawal.
- The participant or their LAR chooses to withdraw.

In such cases, data collected up to the point of withdrawal will be retained and analyzed, unless the participant explicitly requests that their data be destroyed and excluded from the analysis. If a participant requests withdrawal after data collection and analysis have been completed, the request will be considered on a case-by-case basis.

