Study Population	Inpatients admitted to ICU and started on antibiotic treatment within the preceding 72 hours (approximately 3 days).
Control	Results of BV test masked
Randomization	Randomly assigned 1:1 ratio to either the control group or the intervention group.
Primary Objective	To evaluate the combined endpoint of efficacy and safety at 28 days (approximately 4 weeks). This will include: 
 1. Efficacy: Assessed by the use of antibiotics. 2. Safety: Assessed by clinical outcomes. The assessment at 28 days will determine the overall effectiveness and safety of the intervention.
Secondary Objectives	To evaluate antibiotic-free days in ICU, use of reserve/restricted antibiotics, adherence to recommendations; incidence of clinically significant (grade IV) adverse events, recurrent infections, infectious complications, length of stay in ICU, death, colonization with multi-drug-resistant organisms.
Primary Outcome	To evaluate the combined endpoint of efficacy and safety at 28 days (approximately 4 weeks) using Desirability of Outcome

	Ranking (DOOR) and Response Adjusted for Antibiotic Risk (RADAR).
Secondary Outcomes	To evaluate the following parameters; antibiotic-free days in ICU, adverse events, adherence to treatment recommendations, death, and length of stay in ICU.
Exploratory Outcomes	To assess the incidence of colonization or infection with drug-resistant organisms.
Interventional arms	Treatment decision matrix (intervention) plus standard of care compared to standard of care alone (control).
Duration of Intervention	1 Day (BV testing)
Statistical Analysis	Wilcoxon-Mann-Whitney statistic with a 2-sided 95% CI to compare differences between groups, specific to each component and comparison of DOOR distribution between groups. Descriptive analyses for secondary outcomes, and modeling to examine impact of confounding factors. Chi-Square tests will be used for categorical measures and t-tests or Wilcoxon tests for continuous measures.

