7.3 Unblinding at the Intervention Stage

The results of the MeMed BV test, a diagnostic tool used in the study, will only be disclosed for participants in the experimental group. This means that only those in the experimental arm and their treating teams may have access to this specific information, which may influence their treatment. The study and treating team will be informed of the treatment group assignment when the intervention begins, specifically when the clinical assessment is completed.

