9. CLINICAL AND LABORATORY EVALUATIONS

9.1 Clinical Evaluations

After informed consent has been obtained, a research member with appropriate training will record the listed information on the eCRF. The initial evaluation will document reasons for ICU admission, current presentation and symptoms, working diagnosis, the reason for antibiotic therapy, and results of laboratory and diagnostic investigations. Patients will be monitored for 28 days or until death, with an End of Study Visit (EOSV) conducted at the conclusion.

Data collected during follow-up visits will include antibiotic prescriptions, symptoms of infections, laboratory and radiological results from the treating team, and adverse events. Antibiotic data will be extracted from the APSS (Lumed) application, while clinical diagnosis and evolution data will be sourced from patient charts and direct observation. Adverse events will be reported as part of the primary safety outcome.

All data will be collected on an electronic case report form (CRF). Original study forms (source documents) will be kept on file at the study site. All data will be kept for at least 7 years after the study's close.

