10. RISK MANAGEMENT

10.1 Risk Management

We have implemented several procedures to minimize potential risks to participants. These include:

- Specific study inclusion and exclusion criteria to minimize risks for specific high-risk populations
- Participants will have one additional blood sample (about 3-5mL) to be combined with usual bloodwork, on the day of enrollment. The risk of blood sampling includes bleeding, bruising and pain at the drawing site. These risks will be reduced by trying, as much as possible, to collect blood when other standard of care blood tests are being collected.
- The study ensures that standard of care is provided to all participants, with the clinician making final treatment decisions. While the study team's recommendations on antibiotic therapy may inform the treating team, they are not obligatory. The study team mitigates risks associated with potentially insensitive or non-specific biomarker assessments by prioritizing clinical judgment and suggesting expert consultations in cases of significant discrepancies.
- Confidentiality risks are minimized by coding participant information and securely storing it in compliance with MUHC REB policies.

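### Withdrawal under Section 6.1 ends outcome collection for randomized participants who deteriorate after Day 1, when there is no study treatment left to stop

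*Protocol*

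**What the plan says.** Section 6.1 opens with "A participant may be withdrawn from the study if they meet the following criteria". Two of the grounds are "It is deemed in the participant's best interest based on the Investigator's clinical judgment" and "A new health condition arises that necessitates withdrawal". Withdrawal by the participant or the legally authorized representative (LAR) is a separate ground, so these two do not depend on consent. The consequence is that "data collected up to the point of withdrawal will be retained and analyzed", unless the participant asks for destruction of the data. Nothing in 6.1 provides for outcome or vital-status collection afterwards.

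The synopsis gives the duration of the intervention as one day of BV testing. Section 10.1 says of the output: "While the study team's recommendations on antibiotic therapy may inform the treating team, they are not obligatory". Section 9.3 rules out further study blood work. On knowledge of the arm, Section 7.3 says: "The study and treating team will be informed of the treatment group assignment when the intervention begins".

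For follow-up, Section 9.1 says: "Patients will be monitored for 28 days or until death". Section 12.1 states that every participant receives a DOOR, Section 12.7 makes the primary analysis intent-to-treat, and Section 12.9 expects negligible missing data.

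**The concern.** In a drug trial, withdrawing an ill participant can protect that person by stopping the study drug. Here the treating team decides on antibiotics throughout, and the study's contribution is complete once the Day 1 recommendation is in the chart. For a randomized participant, what remains is observation, plus a diary and a remote call for those discharged early. Withdrawal at that stage stops the observation and changes little else.

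The patients affected are not a random subset. A new illness in an ICU patient whose antibiotics were stopped or continued on advice may be related to treatment failure, recurrence, an infectious complication, a Grade IV adverse event or death, which are the components of the DOOR in 12.2. The investigator who judges best interest knows the arm. Missingness can therefore depend on prognosis and can differ by arm.

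At stake is the safety claim (H2), which rests on a 4-point margin. Events lost from the BV arm push the comparison towards non-inferiority and are also not visible to the DSMC. Sections 11 and 11.2 say that events belonging to the primary safety outcome are not reported a second time as AEs or SAEs, so no parallel channel is assured.

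**Working it through.** **Reading the sections together**

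- After Day 1, 6.1 permits an end to data collection that 9.1, 12.1 and 12.7 do not anticipate.
- Section 8.7 asks for every effort to complete Day 28, but for participants discharged early, not for those withdrawn.
- Section 12.9 keeps participants lost to follow-up in the ITT analysis and adds a sensitivity analysis. Its examples are lost charts and deleted records. A sensitivity analysis can probe the bias but cannot recover a death that was never recorded.

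**Inputs**

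- 600 per group (4.1); 4-point margin and an expected adverse outcome rate of 18–20% (12.4); one-sided 0.05 and 80% power (Appendix I).
- Share *w* of event patients lost through withdrawal: not given in the protocol. Assumed 5%, 10% and 20%.
- True risks assumed at the margin: 24% BV, 20% control, that is 144 and 120 expected events in 600.

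**The plan's own figure.** For 18% against 20% with a 4-point margin:

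n = (1.645 + 0.842)² × (0.20×0.80 + 0.18×0.82) / (0.04 + 0.02)² = 6.183 × 0.3076 / 0.0036 = 528.3, which rounds up to the stated 529 per group.

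**Effect of loss.** With the same approximation at 600 per group:

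P(declare non-inferiority) = Φ[(0.04 − (pB − pC)) / SE − 1.645], where SE = √{[pB(1−pB) + pC(1−pC)] / 600}.

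- No loss: pB − pC = 0.04, so P = Φ(−1.645) = 0.05.
- 10% lost, BV arm only, counted event-free: pB = 0.24 × 0.90 = 0.216; difference 0.016; SE = 0.0234; P = Φ(0.024/0.0234 − 1.645) = Φ(−0.62) = 0.27.
- 10% lost in both arms: pB = 0.216, pC = 0.180; difference 0.036; SE = 0.0230; P = Φ(0.004/0.0230 − 1.645) = Φ(−1.47) = 0.07.
- If withdrawn patients are excluded instead, each risk becomes p(1−w)/(1−pw).

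| Share of event patients lost (BV / control) | Events lost (BV / control) | False non-inferiority, counted event-free | False non-inferiority, excluded |
|---|---|---|---|
| 0 / 0 | 0 / 0 | 0.050 | 0.050 |
| 5% / 5% | 7.2 / 6.0 | 0.059 | 0.055 |
| 10% / 10% | 14.4 / 12.0 | 0.071 | 0.061 |
| 20% / 20% | 28.8 / 24.0 | 0.100 | 0.078 |
| 10% / 5% | 14.4 / 6.0 | 0.149 | 0.117 |
| 5% / 0 | 7.2 / 0 | 0.128 | 0.105 |
| 10% / 0 | 14.4 / 0 | 0.267 | 0.197 |
| 20% / 0 | 28.8 / 0 | 0.673 | 0.505 |

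For scale, the 4-point margin equals 0.04 × 600 = 24 patients in one arm.

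**The case against.** Several points on the other side stand and limit the concern.

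- **The criterion is qualified.** The condition must necessitate withdrawal, and the opening wording is permissive. A reader might infer that any participant who becomes septic on Day 5 must or will be withdrawn. The text does not say so. It also does not define what would necessitate withdrawal.
- **The triggering event is retained.** If the new condition is itself a recurrence, complication, failure or Grade IV event, it precedes the withdrawal and lies in the retained data. For a binary combined outcome that patient already counts. What is lost is a later death, a worse DOOR rank, or a first event when the trigger was not an outcome.
- **No favourable rank is assigned to missing data.** A reader might infer that a withdrawn participant lands in Rank 1. Section 12.2 requires survival and clinical benefit for that rank, and a blinded panel reviews outcomes. No section counts missing outcomes as event-free. That handling may be settled in the SAP, so the event-free column above is an assumption.
- **Section 6.1 is not confined to randomized patients.** It can also cover pilot participants and the time between consent and randomization, where withdrawal costs no randomized follow-up. It can also relieve a newly ill participant of the diary and call. To say that the rule can only cut short safety follow-up would be too strong.
- **The new-condition ground names no decision-maker.** Only the best-interest ground names the investigator.
- **Withdrawal clauses are ordinary exceptions to a follow-up schedule.** This softens the clash with 9.1. It does not explain why record-based outcomes should stop when no study treatment is being stopped.

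**Conclusion.** The concern holds for randomized participants after Day 1. As written, 6.1 allows outcome collection to end for reasons linked to prognosis, with the arm known and without the participant's request, and nothing in the protocol restores the later outcomes.

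The size cannot be estimated from the protocol. Under the stated assumptions it is modest if loss is equal in both arms (about 0.06–0.10 against a nominal 0.05) and serious if it is confined to the BV arm (about 0.13–0.67). It is lower in every case if withdrawn patients are excluded rather than counted event-free. The upper figures are an extreme, because they need a true risk exactly at the margin, no loss in control, and up to 20% of BV-arm event patients lost before their event is recorded. They should not be read as a forecast. With follow-up continued to Day 28 or death, the rate stays at 0.05.

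**What to change.** Keep the withdrawal criteria. Removing the best-interest ground is unnecessary and debatable, since it is a participant safeguard in a trial that enrols patients without capacity through a LAR.

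Add to 6.1 that, for randomized participants, any withdrawal other than withdrawal of consent by the participant or LAR, or termination of the study, ends only active study contact (diary and calls). Day 28 vital status, antibiotic use and DOOR events are still taken from the routine record and analysed under ITT. Report withdrawals by arm and reason to the DSMC.

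The cost is a short amendment and consent wording that covers continued record review. No visits or samples are added, and the participant's right to withdraw consent or request destruction of data is unchanged. The amendment should come early, because analysis cannot recover outcomes that were not collected.

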7. RANDOMIZATION AND BLINDING PROCEDURES

7.1 Randomization

Eligible participants will be randomized in a 1:1 ratio to either the intervention or control groups. Randomization will be stratified by study center to account for site-specific participant characteristics and physician practices. This stratification ensures that any potential confounding factors associated with the different sites are balanced across the treatment groups.

To further ensure the randomization process is robust, block randomization will be utilized within each site. The blocks will have varying sizes, determined by an internet-based randomization tool, to prevent predictability and maintain the integrity of the allocation process. The specific block sizes will remain undisclosed to the research team and participants to ensure concealment and prevent potential bias.

7.2 Blinding during Enrollment and Clinical Assessments

[figure not shown]
All team members remain blinded during the Enrollment and Clinical Assessment Stages. The study team, (PI/CO-Is that are ID physicians, pharmacist, and laboratory technologist performing BV testing), will remain blinded while conducting the clinical assessment and laboratory testing.

7.3 Unblinding at the Intervention Stage

The results of the MeMed BV test, a diagnostic tool used in the study, will only be disclosed for participants in the experimental group. This means that only those in the experimental arm and their treating teams may have access to this specific information, which may influence their treatment. The study and treating team will be informed of the treatment group assignment when the intervention begins, specifically when the clinical assessment is completed.

8. STUDY PROCEDURES

8.1 Study Flow Chart

8.2 Schedule of Events

Procedures	Screening	Day 0	Day 1 ¹	Day 3	Day 7	Day 14	Day 28
Visit Window	-3 days			± 1 day	± 1 day	± 1 day	+ 2 days
Enrollment							
Informed Consent	X						
Eligibility Assessment	X						
Randomization			X				
Interventions							
Prescription assessment		X					
Research Blood Collection for BV Testing		X					
BV test reporting ²			X				
Treatment recommendation			X				
Assessments							
Demographics	X						
Medical History	X						
Diagnostics/microbiological results	X	X	X	X	X	X	X
Adherence to treatment recommendation				X	X	X	X
Signs/symptoms of infection	X	X	X	X	X	X	X
Antibiotic use	X		X	X	X	X	X
Adverse events, safety outcomes			X	X	X	X	X
Outcome / disposition							X

¹Day 1 is defined as the day of randomization until 11:59 pm of the same day.

²BV test result for intervention group only.

8.3 Screening Period (-3 days to 0 days)

Prior to enrollment, potential participants will be evaluated to determine that they fulfill the entry requirements as set forth in Sections 3.2 and 3.3. Participants are expected to enroll as soon as possible after eligibility is confirmed.

The Investigator will perform a preliminary assessment of the participant's eligibility. Prior to screening, the Investigator or designee will explain the study to the participant/LAR in lay terms. If the participant/LAR consents to participation in the study, during a 1 hour visit the following will be performed:

- Complete the informed consent process with participant/LAR.
- Provide participant/LAR with a copy of signed and dated consent form.
- Assign Participant ID from REDCap.
- Perform the assessment of inclusion/exclusion criteria.
- Obtain the participant's medical history, pre-existing or active conditions.
- Collect the following data on participant:
 - o Demographics: Age, sex, gender, ethnicity, ;
 - o Admission data: date of admission to the hospital and ICU
 - o Medical History
 - o Antibiotic prescription; name of drug, dose, start and end date
 - o Clinical status; vital signs, temperature (T max day -2 to Day 1), ventilation status; need for vasopressor support (type and dose)
 - o Data on infection; site, microbiological results, signs and symptoms of infection
 - o Basic laboratories; hematological, biochemical (routine)
 - o Imaging; pertinent X-ray and/or CT scans
 - o Baseline status of MDRO colonization: swab results for MRSA, VRE, CPE

8.4 Baseline Visit (Day 0)

Study team (Pharmacist and PI/Co-I) perform a clinical assessment of the participant to establish a baseline assessment of the antibiotic prescription (indication and appropriateness of antibiotic) and enter the assessment into the eCRF.

- Collect the following data on participant:
 - o Antibiotics prescribed (start and end dates, name, dose)
 - o Microbiological results
 - o Colonization status for MDRO
 - o Signs and symptoms of infection
 - o Adverse events related to antibiotics if any
 - o Laboratory values for creatinine, liver, hematology
- Research Blood Collection; Collect up to 5 mL (1 teaspoon) of blood for research laboratory BV testing and analysis

8.5 Randomization and Intervention (Day 1)

Study team will enter study ID in randomization system and obtain a study group assignment. Based on the assignment, BV test result is communicated to the blinded team.

The study team (Pharmacist and PI/Co-I) finalize treatment recommendation for both groups (BV value only available for the intervention group) by placing the recommendation in the medical chart.

- Collect the following data on participant:
 - Antibiotics prescribed (start and end dates, name, dose)
 - Microbiological results
 - Colonization status for MDRO
 - Signs and symptoms of infection
 - Adverse events related to antibiotics if any
 - Laboratory values for creatinine, liver, hematology

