8.9 Antibiotic treatment decision procedure specific to the control group

For the control group, the BV test result will remain masked to investigators and treating team members.

The antimicrobial stewardship study team (Pharmacist and PI/Co-I) will issue antibiotic treatment suggestions following the standard decision matrix outlined below. The recommendation will be shared with the treating team.

Necessity of antibiotics	Recommendation on antibiotic treatment
Clearly not indicated	STOP (strong recommendation)
Somewhat indicated	Stop (moderate recommendation) or continue --> review choice*
Indicated (Justified)	Continue antibiotic --> review choice *
Cannot be rated	Consider expert (ID) consultation

For all cases where necessity of antibiotics was rated as “somewhat indicated” or “indicated”, the choice of antibiotics will be rated. The final recommendation (to stop, continue or change antibiotic) is shared with the treating team.

Choice of antibiotic	Recommendation on antibiotic treatment
Far too broad	Change drug (strong recommendation)
Somewhat too broad	Consider changing drug (moderate recommendation)
Appropriate choice	Continue same drug
Somewhat too narrow	Change drug
Cannot be rated	Consider expert consultation (ID)

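### Control-arm advice is finalised after the study team knows the allocation, and one row of the control matrix leaves stop or continue open, so the antibiotic-days comparison is exposed to bias in either direction

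*Protocol*

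**What the plan says.** **Before allocation.** Protocol 7.2 limits blinding to the first stages: "All team members remain blinded during the Enrollment and Clinical Assessment Stages". On Day 0 (8.4) the pharmacist and PI/Co-I make a "baseline assessment of the antibiotic prescription (indication and appropriateness of antibiotic) and enter the assessment into the eCRF". Section 8.8 applies to all participants and lists three rated domains: diagnostics, necessity and choice of antibiotic. The schedule in 8.2 places the prescription assessment on Day 0, and randomization, BV reporting and the treatment recommendation on Day 1.

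**At allocation.** Section 8.5 opens Day 1 with "Study team will enter study ID in randomization system and obtain a study group assignment". The BV result is then released according to arm, and the same pharmacist and PI/Co-I "finalize treatment recommendation for both groups (BV value only available for the intervention group) by placing the recommendation in the medical chart". Section 7.3 agrees: "The study and treating team will be informed of the treatment group assignment when the intervention begins, specifically when the clinical assessment is completed".

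**The two matrices.** In the control arm the stewardship study team "will issue antibiotic treatment suggestions following the standard decision matrix outlined below" (8.9). Two necessity rows have a fixed direction: clearly not indicated gives stop, indicated gives continue. The somewhat-indicated row reads "Stop (moderate recommendation) or continue". An unratable prescription leads to considering a consultation, and a somewhat too broad choice leads to considering a change of drug. In 8.10 every combination of necessity rating and BV band has one output.

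**The concern.** H1 compares mean antibiotic days between arms (12.4, 12.9). Controls receive active stewardship advice, so their antibiotic days depend partly on that advice. Where the matrix leaves the advice open, the people choosing it know that the patient is a control. A lean towards continue among known controls would add to the apparent BV effect. A lean towards stop would subtract from it.

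Section 1.3 makes the control arm's behaviour part of the interpretation. If exposure is not reduced, the investigators will ask whether unexpectedly low control-arm use explains it, and may then recommend either BV testing or clinical assessment alone. That reading is secure only if control advice was set without knowledge of the arm. The order of randomization and recommendation is trial conduct fixed in sections 7 and 8. No later analysis can supply a pre-allocation recommendation that was never recorded.

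**Working it through.** **1. Order of steps.** Rating entered, blind (7.2, 8.4); assignment obtained by the study team (8.5); BV result released by arm (8.5); recommendation finalised for both arms (8.5). No section asks for a recommendation to be recorded before the assignment, or to be made by someone unaware of it. Section 8.5 does describe the team receiving the BV result as blinded. But the same paragraph has the study team obtain the assignment, 7.3 says it is told, and the presence or absence of a BV value reveals the arm.

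**2. Where discretion lies.** For a somewhat-indicated rating, 8.10 gives stop, stop or continue according to BV band; 8.9 gives stop or continue with no rule. The open stop/continue choice exists only in the control arm.

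**3. The plan's own H1 figure.** Inputs from 12.4: difference 1.5 days, SD 8, one-sided 0.05, power 80%.

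n per group = 2 × (1.645 + 0.842)² × 8² / 1.5² ≈ 352, as stated.

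At the planned 600 per group (4.1), SE = 8 × √(2/600) = 0.462 days. Power = Φ(1.5/0.462 − 1.645) ≈ 94.6%.

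**4. Size of a possible shift.** Shift in control mean = share of controls in the open row × net share switched by knowledge of the arm × days separating stop from continue × share of advice followed.

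Section 12.4 gives only about 30% for clearly-not and only-somewhat indicated combined. All four inputs below are therefore assumptions.

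| Case | In row | Switched | Days | Followed | Shift (days) | % of 1.5 |
|---|---|---|---|---|---|---|
| Low | 0.10 | 0.25 | 3 | 0.5 | 0.04 | 2.5 |
| Mid | 0.15 | 0.375 | 4 | 0.6 | 0.14 | 9 |
| Upper | 0.20 | 0.50 | 5 | 0.7 | 0.35 | 23 |

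**5. Effect on the H1 test at 600 per group, SD 8.**

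- If the contrast is widened and BV has no true effect, false rejection = Φ(shift/0.462 − 1.645): about 6% (low), 9% (mid) and 19% (upper), against a nominal 5%.
- If the contrast is narrowed and the true effect is 1.5 days, power = Φ((1.5 − shift)/0.462 − 1.645): about 94% (low), 90% (mid) and 80% (upper).

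These figures cover the open stop/continue row only. The 'consider' entries are not quantified.

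**The case against.** Much of the process is protected. The necessity rating is blind and recorded before allocation, two of the four necessity rows have a fixed direction, and 10.1 makes the advice non-binding, so any effect is diluted by adherence. All of this stands and limits the size. It does not close the open row.

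Four stronger readings are tempting, and the documents do not support them.

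- **That the unblinded team itself sets the difference between arms.** It influences one row, plus some softer wording, of advice that the treating clinician may decline.
- **That the antibiotic-choice rating is made with the arm known.** Section 8.8 includes choice in the assessment of all participants, and 8.2 and 8.4 put that assessment on Day 0. Sections 8.9 and 8.10 describe rating choice as a step within the matrix, which makes the timing ambiguous and no more than that.
- **That drift could never be seen.** The rating is recorded on Day 0, and 8.11 collects the recommendation, its date and adherence. The stop/continue split among somewhat-indicated controls can therefore be tabulated. What is missing is a pre-allocation recommendation to compare it with.
- **That the bias could consume most of the 1.5-day effect.** A shift of 1.4 days (0.20 × 7 days × full adherence) requires every recommendation in the row to flip one way. That is a ceiling on what the row could do, not an estimate.

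It is also fair to say that even 0.35 days needs all four upper limits together, with all switching in one direction, and that narrowing by that amount still leaves about 80% power. The greater exposure is to false rejection.

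**Conclusion.** The point holds in limited form. The order (assignment, then recommendation) and the open control row are explicit in the Protocol. Following it as written therefore allows knowledge of the arm to affect control advice, and through it the H1 contrast, in either direction. Confidence in the mechanism is high. The size is not known from the documents: 0.04 to at most 0.35 days, mid-range about 0.14, under the four assumed inputs. The sample sizes are not in dispute. The change should be made because it is cheap and removes a bias that analysis cannot undo.

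**What to change.** Amend 8.4 and 8.5 as follows.

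1. Before the assignment is requested, record and time-stamp in the eCRF the full control-matrix recommendation for every participant, including a single stop-or-continue choice for the somewhat-indicated row. Which option is chosen remains the team's clinical judgement.
2. State that the choice rating used in 8.9 and 8.10 is the one made on Day 0 under 8.8.
3. After allocation, issue the locked recommendation in the control arm, and apply the BV matrix to the locked ratings in the experimental arm.
4. Allow a change only for new clinical information arising after the lock (8.5 collects microbiology and laboratory values on Day 1), under the same rule in both arms, and log it with the reason.
5. Keep the locked version, and compare locked with issued advice by arm.

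Cost: one extra locked form before randomization and a few sentences in 8.4 and 8.5. The same team makes the same assessment, and the sample size is unchanged.
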